1.6.4 Alpha fetoprotein (AFP) tumor marker

The most commonly measured blood tumor marker of HCC is AFP, a glycoprotein highly expressed during hepatocyte development. AFP is secreted by approximately 70% of HCC. Elevated baseline AFP levels have been shown to correlate with worse prognosis after hepatic resection, transplant, and local therapies. A study of patients enrolled in a phase III randomized trial comparing two palliative cytotoxic chemotherapy regimens showed that patients with AFP decline by at least 20% (designated as AFP responders) demonstrated markedly improved survival by comparison with AFP non-responders, with overall survival 13.5 versus 5.6 months, respectively (p < 0.0001). AFP changes are also associated with response to sorafenib and may be an early surrogate marker of response. 36,37

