8.2.3 Exploratory endpoints

For exploratory endpoints, due to the small sample size in the study, descriptive statistics with mean and 95% confidence intervals will be used. Depending on funding availability, we plan to explore immunologic and genomic biomarkers (including PBMC T cell subsets and TCR frequency and diversity, tumor immune subset composition and immune infiltrates) for relationships to clinical features including etiology of liver disease, baseline liver function, and to the primary and secondary efficacy endpoints. No type I error will be adjusted for multiple endpoints. For continuous variables, descriptive statistics will include the number of non-missing values, mean, standard deviation, median, min and maximum. For categorical variables, descriptive statistics will include counts and percentages per category. For comparison between subgroups, ANOVA and t-tests will be used when appropriate to determine the association of the efficacy endpoints and the specific biomarkers. For association between biomarkers, Spearman correlations will be calculated to determine the significance of the association between the biomarkers of interest. A selection of planned analyses is described further below.

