8.2.3.4 Tumor and immune cell PD-L1 expression

Tumor and immune cell PD-L1 expression will be tested in batch after completion of enrollment. The proportion of subjects with archival tumor samples positive for PD-L1 or

PD-L1 and CD-45 expression by IHC will be reported along with 95% CI. For subjects with more than one tumor sample available for testing, designation as positive for PD-L1 expression will be based upon ≥1 positive sample. Concordance and rates of positivity between primary and metastatic site, tumor location (e.g. liver vs. non-liver), etiology (e.g. viral vs. nonviral), and pre-treatment, , and post-treatment samples (if available) will be described individually due to expectation of small subset/paired sample sizes. PD-L1 expression status in tumor and immune cells will be explored for association with ORR, PFS, and OS.

Tumor and IC PD-L1/CD45 analyses will be performed in UCSF CIL or other laboratory approved by Study Chair dependent upon funding and sample availability.

8.2.3.5 **AFP response**

Among patients with baseline AFP \geq 20 ng/mL, baseline AFP levels (using various cut points from literature) will be explored for association with ORR, PFS, and OS using Fisher's Exact tests or by Wilcoxon Rank-Sum test. Changes in levels on therapy will be measured as an increase by \geq 20% and \geq 50% from baseline, stable value within 20% and 50% of baseline, or decrease by \geq 20% and \geq 50% from baseline. The changes in level will be used to evaluate the predictive value for ORR, PFS, or OS.

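### Section 8.2.3.5 states no full-scale analysis of AFP for PFS or OS, or of AFP change for any outcome; unnamed cuts cost power and, for survival outcomes, invite chance findings

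*Combined protocol and SAP*

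**What the plan says.** Section 8.2.3.5 restricts the analysis to patients with baseline AFP of at least 20 ng/mL.

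- **Baseline AFP:** "baseline AFP levels (using various cut points from literature) will be explored for association with ORR, PFS, and OS". Neither the number nor the values of the cuts are given. The tests named are Fisher's exact "or by Wilcoxon Rank-Sum test".
- **On-treatment change:** sorted into increase, stable and decrease, each at two thresholds; the middle class is a "stable value within 20% and 50% of baseline". Neither threshold is primary and no test is named. The stated aim is nevertheless inferential: "The changes in level will be used to evaluate the predictive value for ORR, PFS, or OS".
- **Background (section 1.6.4):** the one threshold spelled out is a 20% fall, where "patients with AFP decline by at least 20% (designated as AFP responders) demonstrated markedly improved survival". Two studies of AFP change on sorafenib are also cited, without thresholds.
- **General rule (section 8.2.3):** "descriptive statistics with mean and 95% confidence intervals will be used", with ANOVA and t-tests for subgroup comparisons, and "No type I error will be adjusted for multiple endpoints".

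AFP is measured at screening and on Day 1 of every cycle (section 7.1 footnotes). No regression on AFP appears in section 8.

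**The concern.** AFP is a continuous measurement. Cutting it treats patients just either side of a threshold as different and all patients on one side as alike. With few patients, that discards information the trial cannot spare.

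The cuts are also plural and open. A 30% fall is a decrease at the 20% threshold and stable at the 50% threshold. Nesting two levels is not itself an error, but with neither marked as primary, the choice of which to report is left until the data are seen. The same holds for the baseline cuts.

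Exploratory objective 7 in section 2.3 (AFP changes and clinical outcomes) could therefore be answered with avoidable loss of power and an inflated chance that some cut looks predictive. The ambiguity also spreads: sections 1.6.2, 1.6.3 and 8.2.3.3 use AFP response as an outcome for the immune markers, yet section 8.2.3.5 adopts neither threshold as its definition.

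**Working it through.** The plan gives no power, effect size or alpha for AFP, so there is no figure to reproduce. What follows is a sizing under stated assumptions.

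**Inputs**
- Patients: at most 24 (section 8.4). About 70% of these tumours secrete AFP (section 1.6.4), so 0.70 × 24 = 16.8, about 17. This assumes that secreting AFP means a baseline of at least 20 ng/mL.
- Effect: median OS of 13.5 and 5.6 months for AFP responders and non-responders (section 1.6.4), from a chemotherapy trial.
- Assumed: normal log AFP change, linear in the log hazard; censoring uniform over 12 to 36 months; two-sided 5%.

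**Step 1. Effect per SD.** ln(13.5/5.6) = 0.880. For a normal marker cut at quantile q, the group means differ by φ(z_q)/[q(1−q)] SD, which is 1.656, 1.610 and 1.596 for q = 0.3, 0.4 and 0.5. Dividing gives 0.53, 0.55 and 0.55; calibrating by simulation gives 0.52 to 0.54. Value used: 0.53.

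**Step 2. Efficiency of one cut.** The large-sample efficiency is φ(z_q)²/[q(1−q)], which is 0.576, 0.622 and 0.637 for the same q. If the continuous test has 42% power, its noncentrality is 1.96 − 0.20 = 1.76. Multiplying by the square root of the efficiency gives 1.33, 1.39 and 1.40, so power falls to about 27%, 28% and 29%: a loss of 13 to 15 points.

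**Step 3. Simulation for OS, n = 17** (Cox score test on the uncut marker against log-rank at one cut):

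| Share below cut | Continuous | One cut | Loss |
|---|---|---|---|
| 30% | 41% | 22% | 19 |
| 40% | 41% | 27% | 14 |
| 50% | 41% | 30% | 11 |

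Independent repeats gave 40–43% against 24–31%. With n = 24 the figures are 55–56% against 31%, 37% and 40%.

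**Step 4. How far the loss varies.** With a median cut and no censoring, changing the log hazard ratio from 0.3 to 0.9 per SD moves the OS loss from 4 to 20 points at n = 17; at n = 12 with the weakest effect it is about 1 point. For ORR at 15%, n = 24 and a 2.0 SD shift, Wilcoxon on uncut AFP has 74% power against 12% for Fisher at the median: 62 points.

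**Step 5. Chance findings for OS.** Four change cuts (−50%, −20%, +20%, +50%), each tested by log-rank with no true association, n = 17 or 24, SD of the log ratio 0.5 to 1.2: at least one is significant in about 16 to 25% of trials, against about 6% for one continuous test. Four independent tests would give 1 − 0.95⁴ = 18.5%. The cuts are correlated, but the log-rank approximation is slightly liberal at this size.

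**Step 6. Chance findings for ORR.** The best of three baseline cuts by Fisher is significant in only 2 to 5% of null trials, because Fisher's test is conservative with few responders. There is no inflation to correct there.

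**The case against.** A reader might infer that AFP is analysed only through cuts. The documents do not support that for baseline AFP. The same sentence names a Wilcoxon rank-sum test, which can compare uncut AFP between responders and non-responders, and section 8.2.3 permits t-tests and ANOVA. The wording is ambiguous, since Wilcoxon could instead compare outcomes between AFP groups, but ambiguity is not absence. This answer stops at ORR: Wilcoxon compares two groups, so with censored PFS or OS either AFP or the outcome must be cut. It is also not offered for AFP change.

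A reader might also infer that the ±50% classes lack any published support. That cannot be said. Section 1.6.4 cites two further sorafenib studies whose thresholds are not visible in the documents.

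The sizing can be challenged too. Linearity in the log hazard favours the continuous test, the effect is borrowed from chemotherapy, and section 8.2.3.5 does not name log-rank. If PFS and OS were instead split at their medians and tested by Fisher, three assumed baseline cuts across three outcomes would give a 5 to 16% chance of a false positive. So the figures illustrate; they are not properties of the plan.

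Finally, the lack of adjustment is declared, the analysis is exploratory, and no dose or go/no-go decision uses AFP. All of that stands and lowers the weight. It does not settle which cut will be reported.

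**Conclusion.** The point holds in a limited form. AFP change is described only in classes, the baseline cuts are unnamed, and no full-scale analysis is stated for PFS, for OS, or for change.

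For OS with 17 patients, a log hazard ratio of about 0.53 per SD and linearity, one cut costs roughly 11 to 19 points of power. Testing four change cuts by log-rank gives about a 16 to 25% chance of a false positive, against about 6%. A reader might take the power loss as general; it is not, since it runs from about 1 to 62 points across the endpoints, sizes and effects examined. Nor does the false-positive concern extend to ORR tested by Fisher.

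Weight is low. With about 17 patients, and 2 to 3 responders at an ORR of 15% (0.15 × 17 = 2.6), no method gives a firm answer. The change is still worth making because it is specific and nearly free.

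**What to change.** In section 8.2.3.5:

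1. Make the main exploratory analysis continuous: log baseline AFP, and the log ratio to baseline of AFP at one on-treatment visit named in advance.
2. For ORR, use the Wilcoxon rank-sum test and state that it is applied to uncut values.
3. For PFS and OS, use Cox models with the log value as a single covariate. Landmark the change analysis at the named visit; without a fixed time point the covariate is undefined.
4. Keep the cited decline of at least 20% as the single AFP-response class, here and in the sections that use AFP response as an outcome.
5. Report any ±50% classes or other cuts descriptively, without tests.

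This leaves six unadjusted tests (two markers by three outcomes), which should be labelled exploratory.

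The cost is wording only, since AFP is already collected on Day 1 of every cycle. There are two drawbacks. An effect per doubling is less familiar to clinicians than a responder class, which is why the 20% class stays. Patients with an event before the landmark drop out of the change analysis, so their number should be reported.

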8.3 Planned interim analyses

8.3.1 Part 1: Dose Escalation Cohort DLT analyses

In Part 1, a standard 3+3 design for dose escalation and expansion decisions will be used as described above.

8.4 Determination of sample size

The total sample size will be 6-24 patients for Parts 1 and 2 combined.

8.4.1 Part 1: Dose Escalation Cohort sample size

It is estimated that 6-12 patients will be enrolled to Part 1 following 3+3 dose escalation rules in Section 6.2.2.

8.4.2 Part 2: Child Pugh B Expansion Cohort sample size

The Part 2 expected evaluable sample size is n=12 patients.

9. Data handling and quality assurance

9.1 Pre-study documentation

This study will be conducted in accordance with the ethical principles that have their origin in the Declaration of Helsinki as stated in 21 CFR §312.120(c)(4); consistent with GCP and all applicable regulatory requirements.

Before initiating this trial, the Investigator will have written and dated approval from the Institutional Review Board for the protocol, written informed consent form, subject recruitment materials, and any other written information to be provided to subjects before any protocol related procedures are performed on any subjects.

The clinical investigation will not begin until either FDA has determined that the study under the Investigational Drug Application (IND) is allowed to proceed or the Investigator has received a letter from FDA stating that the study is exempt from IND requirements.

The Investigator must comply with the applicable regulations in Title 21 of the Code of Federal Regulations (21 CFR §50, §54, and §312), GCP/ICH guidelines, and all applicable regulatory requirements. The IRB must comply with the regulations in 21 CFR §56 and applicable regulatory requirements.

9.2 Institutional Review Board approval

The protocol, the proposed informed consent form, and all forms of participant information related to the study (e.g. advertisements used to recruit participants) will be reviewed and approved by the UCSF IRB (UCSF Institutional Review Board). Prior to obtaining IRB approval, the protocol must be approved by the Helen Diller Family Comprehensive Cancer Center Gastrointestinal Oncology Site Committee and by the Protocol Review Committee (PRC). The initial protocol and all protocol amendments must be approved by the IRB prior to implementation.

9.3 Informed consent

All participants must be provided a consent form describing the study with sufficient information for each participant to make an informed decision regarding their participation. Participants must sign the IRB-approved informed consent form prior to participation in any study specific procedure. The participant must receive a copy of the signed and dated consent document. The original signed copy of the consent document must be retained in the medical record or research file.

9.4 Changes in the protocol

Once the protocol has been approved by the UCSF IRB, any changes to the protocol must be documented in the form of an amendment. The amendment must be signed by the Investigator and approved by PRC and the IRB prior to implementation.

If it becomes necessary to alter the protocol to eliminate an immediate hazard to patients, an amendment may be implemented prior to IRB approval. In this circumstance, however, the Investigator must then notify the IRB within writing within five (5) working days after implementation. The Study Chair and the UCSF study team will be responsible for updating any participating sites.

9.5 Handling and documentation of clinical supplies

The UCSF Principal Investigator and each participating site will maintain complete records showing the receipt, dispensation, return, or other disposition of all investigational drugs. The date, quantity and batch or code number of the drug, and the identification of patients to whom study drug has been dispensed by patient number and initials will be included. The sponsor-investigator will maintain written records of any disposition of the study drug.

The Principal Investigator shall not make the investigational drug available to any individuals other than to qualified study patients. Furthermore, the Principal Investigator will not allow the investigational drug to be used in any manner other than that specified in this protocol.

9.6 Case report forms (CRFs)

The Principal Investigator and/or his/her designee, will prepare and maintain adequate and accurate participant case histories with observations and data pertinent to the study. Study specific Case Report Forms (CRFs) will document safety and treatment outcomes for safety monitoring and data analysis. All study data will be entered into OnCore® via standardized CRFs in accordance with the study calendar, using single data entry with a secure access account. The CRC will complete the CRFs as soon as possible upon completion of the study visit; the Investigator will review and approve the completed CRFs.

The information collected on CRFs shall be identical to that appearing in original source documents. Source documents will be found in the patient's medical records maintained by UCSF personnel. All source documentation should be kept in separate research folders for each patient.

In accordance with federal regulations, the Investigator is responsible for the accuracy and authenticity of all clinical and laboratory data entered onto CRFs. The PI will approve all completed CRFs to attest that the information contained on the CRFs is true and accurate.

All source documentation and OnCore data will be available for review/monitoring by the UCSF DSMC and regulatory agencies.

The Principal Investigator will be responsible for ensuring the accurate capture of study data. At study completion, when the CRFs have been declared to be complete and accurate, the database will be locked. Any changes to the data entered into the CRFs after that time can only be made by joint written agreement among the Study Chair, the Trial Statistician, and the treating investigator.

9.7 Oversight and monitoring plan

The UCSF Helen Diller Family Comprehensive Cancer Center DSMC will be the monitoring entity for this study. The UCSF DSMC will monitor the study in accordance with the NCI-approved Data and Safety Monitoring Plan (DSMP) for multi-center trials (Appendix 14.11). The DSMC will routinely review all adverse events and suspected adverse reactions considered "serious". The DSMC will audit study-related activities to ensure that the study is conducted in accordance with the protocol, local standard operating procedures, FDA regulations, and Good Clinical Practice (GCP). Significant results of the DSMC audit will be communicated to the IRB and the appropriate regulatory authorities at the time of continuing review, or in an expedited fashion, as applicable. See Appendix 14.11, Data and Safety Monitoring Plan for additional information.

9.8 Multicenter communication

The UCSF Coordinating Center provides administration, data management, and organizational support for the participating sites in the conduct of a multicenter clinical trial. The UCSF Coordinating Center will also coordinate, at weekly conference calls with the participating sites for Phase I dose escalation studies prior to each cohort escalation and at the completion of each cohort or more frequently as needed to discuss risk assessment. The following issues will be discussed as appropriate:

- Enrollment information
- Cohort updates (i.e. DLTs) and enrollment status
- Adverse events (i.e. new adverse events and updates on unresolved adverse events and new safety information)
- Protocol violations
- Other issues affecting the conduct of the study

9.9 Record keeping and record retention

The Principal Investigator is required to maintain adequate records of the disposition of the drug, including dates, quantity, and use by subjects, as well as written records of the disposition of the drug when the study ends. The Principal Investigator is required to prepare and maintain adequate and accurate case histories that record all observations and other data pertinent to the investigation on each individual administered the investigational drug or employed as a control in the investigation. Case histories include the case report forms and supporting data including, for example, signed and dated consent forms and medical records including, for example, progress notes of the physician, the individual's hospital chart(s), and the nurses' notes. The case history for each individual shall document that informed consent was obtained prior to participation in the study.

Study documentation includes all CRFs, data correction forms or queries, source documents, Sponsor-Investigator correspondence, monitoring logs/letters, and

regulatory documents (e.g., protocol and amendments, IRB correspondence and approval, signed patient consent forms). Source documents include all recordings of observations or notations of clinical activities and all reports and records necessary for the evaluation and reconstruction of the clinical research study.

In accordance with FDA regulations, the investigator shall retain records for a period of 2 years following the date a marketing application is approved for the drug for the indication for which it is being investigated; or, if no application is to be filed or if the application is not approved for such indication, until 2 years after the investigation is discontinued and FDA is notified.

9.10 Coordinating Center documentation of distribution

It is the responsibility of the Study Chair to maintain adequate files documenting the distribution of study documents as well as their receipt (when possible). The HDFCCC recommends that the Study Chair maintain a correspondence file and log for each segment of distribution (e.g., FDA, drug manufacturer, participating sites, etc.).

Correspondence file: should contain copies (paper or electronic) of all protocol versions, cover letters, amendment outlines (summary of changes), etc., along with distribution documentation and (when available) documentation of receipt.

Correspondence log: should be a brief list of all documents distributed including the date sent, recipient(s), and (if available) a tracking number and date received.

At a minimum, the Study Chair must keep documentation of when and to whom the protocol, its updates and safety information are distributed.

9.11 Regulatory documentation

Prior to implementing this protocol at UCSF or any participating site, the protocol, informed consent form, and any other information pertaining to participants must be approved by the UCSF IRB. Prior to implementing this protocol at the participating sites, approval of the UCSF IRB approved protocol must be obtained from the participating site's IRB.

The following documents must be provided to UCSF HDFCCC before the participating site can be initiated and begin enrolling participants:

- Participating Site IRB approval(s) for the protocol, informed consent form, and HIPAA authorization
- Participating Site IRB approved consent form
- Participating Site IRB membership list
- Participating Site IRB's Federal Wide Assurance number and OHRP Registration number
- Curriculum vitae and medical license for each investigator and consenting professional
- Documentation of Human Subject Research Certification training for investigators and key staff members at the Participating Site
- Participating site laboratory certifications and normals.

Upon receipt of the required documents, UCSF HDFCCC will formally contact the site and grant permission to proceed with enrollment.

9.12 Audit and inspection

Inspections by regulatory health authority representatives i.e. FDA and IEC(s)/IRB(s) are possible. The investigator should notify Bayer and BMS immediately of any such inspection.

10. Protection of Human Subjects

